3 STATISTICAL ANALYSES

3.1 GENERAL CONSIDERATIONS

This study is not intended to explicitly test a hypothesis. For the primary and secondary efficacy endpoints, 95% CIs will be provided.

All efficacy endpoints based on radiological assessments of tumor burden (ie, ORR, DOR, PFS, and DCR) will be derived using the local radiologist's/Investigator's assessment.

In general, continuous data will be summarized using the number of observations available, mean, standard deviation, median, Q1, Q3, minimum, and maximum. Categorical and ordinal data will be summarized using the count and percentage of participants.

The baseline value is defined as the last available value before the first dose of IMP.

The study cut-off for analysis of the primary endpoint, ORR, corresponds to the date on which all evaluable treated participants have had at least 2 postbaseline tumor assessments, experienced confirmed objective response, or have discontinued the study treatment for any reason. For participants with 2 postbaseline tumor assessments and occurrence of response at the second postbaseline tumor assessment, it will also include the confirmatory assessment. This study cut-off can be up to approximately 20 weeks (16 weeks for 2 tumor assessments and 4 weeks for confirmation of response, if needed) after the last participant's first IMP administration. Of note, DCR will also be assessed at this cut-off.

The final study cut-off for analysis of the secondary efficacy endpoints, which include DOR and PFS, will be 4 months after the cut-off date for the primary analysis. At that time, the primary analysis of ORR and DCR will also be updated.

Observation period

The observation period will be divided into 4 segments:

- The **pre-treatment period** is defined as the period up to first IMP administration.
 - The **pre-screening period** is defined as the period from the pre-screening informed consent to the day before the screening informed consent.
 - The **screening period** is defined as the period from the screening informed consent up to the first IMP administration.
- The **on-treatment period** (ie, treatment-emergent period) is defined as the period from the first IMP administration to 30 days after the last IMP administration.
- The **post-treatment period** is defined as the period from the end of the on-treatment period.

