1.3 SCHEDULE OF ACTIVITIES (SOA)

1.3.1 Study flow chart

Procedure	Pre- screening ^a	Screening ^b	Treatment (Cycle 1	Subsequent Cycles (14 ±2 days from previous infusion)		End of treatment	Follow-up ^d	Notes
Day(D)	Days prior to initial infusion	Days prior to initial infusion	D1 Pre- infusion	D8	D1 Pre- infusion ^c (±2 days)	Every 8 weeks (±7 days)	D30 after last infusion (±5 days)	D90 after last infusion (±7 days)	
Available CEACAM5 expression status (archival tumor tissue) after pre-screening informed consent ^a	≤42								Available CEACAM5 expression results from EFC15858 Study assessed by central IHC will be used after pre- screening informed consent will be signed.
Informed consent		Х							
Circulating CEA ^e	≤42	≤7				X	x	Х	At pre-screening, after pre-screening informed consent signed. Then after informed consent signed. On infusion days, to be performed before infusion or the day before

Procedure	Pre- screening ^a	Screening ^b	Treatment C	Cycle 1	Subseque (14 ±2 da previous	ent Cycles ays from infusion)	End of treatment	Follow-up ^d	Notes
Day(D)	Days prior to initial infusion	Days prior to initial infusion	D1 Pre- infusion	D8	D1 Pre- infusion ^c (±2 days)	Every 8 weeks (±7 days)	D30 after last infusion (±5 days)	D90 after last infusion (±7 days)	
CEACAM5 expression status and RNA/DNA analysis on fresh tumor tissue ^f		≤28							After informed consent signed. Fresh biopsy at screening is optional.
lgG			х						Will be collected at C1D1 pre-infusion only.
Plasma for Circulating CEACAM5 ^g		≤7				Х			
Plasma for tumor cfDNA and whole blood for germline DNA			Х						
IRT contact	Х	Х	Х		Х		Х	Х	
Inclusion and exclusion criteria		≤28	Х						
Demography		≤28							
Medical/surgical/disease history ^h	X ⁱ	≤28							

Procedure	Pre- screening ^a	Screening ^b	Treatment (Cycle 1	Subseque (14 ±2 d previous	ent Cycles ays from infusion)	End of treatment	Follow-up ^d	Notes
Day(D)	Days prior to initial infusion	Days prior to initial infusion	D1 Pre- infusion	D8	D1 Pre- infusion ^c (±2 days)	Every 8 weeks (±7 days)	D30 after last infusion (±5 days)	D90 after last infusion (±7 days)	
Physical examination, ECOG performance status		≤7	Х		X		X	Х	Examination of major body systems including cardiovascular, central nervous system, respiratory system, gastrointestinal system, hepatomegaly, splenomegaly, lymphadenopathy.
Height		≤7							
Weight		≤7	Х		х		x		On Day 1 of each treatment cycle
Vital signs		≤7	Х		х		x		Temperature, blood pressure, and pulse rate

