4 STUDY DESIGN

4.1 OVERALL DESIGN

This is a single group, Phase 2, open-label, multi-center study assessing efficacy (anti-tumor activity), safety, and PK of tusamitamab ravtansine single agent in NSQ NSCLC participants with negative or moderate CEACAM5 expression tumors and high circulating CEA (\geq 100 ng/mL) at baseline.

Moderate CEACAM5 expression is defined as intensity $\geq 2+$ in $\geq 1\%$ and <50% of tumor cells.

Negative CEACAM5 expression is defined as intensity 1+ whatever the percentage of stained tumor cells or <1% of tumor cells.

During the pre-screening phase, participants who were pre-screen failed in the EFC15858 Phase 3 trial with available CEACAM5 status (central assessment by IHC) as negative or moderate expression on archival tumor tissue can be pre-screened. Participants with high circulating CEA (\geq 100 ng/mL) will be screened and will go through protocol screening procedures.

After being screened, the eligible participants will receive tusamitamab ravtansine as a single agent treatment at the dose of 100 mg/m² Q2W until disease progression, unacceptable AE, initiation of a new anticancer therapy, or the participant's or Investigator's decision to stop the treatment, whichever comes first. A total of approximately 38 participants are planned to be treated. An interim analysis is planned after 20 participants treated are evaluable for anti-tumor activity or efficacy. If at least 2 confirmed objective responses are reported, the recruitment will continue to achieve a total of 38 evaluable treated participants.

The duration of the study for a participant will include:

- Pre-screening period: a pre-screening informed consent will be signed in order to collect available CEACAM5 expression results on archival tumor tissue from EFC15858 study and the circulating CEA value.
- Screening period: up to 28 days.
- Treatment period: once successfully screened, enrolled participants may receive study intervention until disease progression, unacceptable AE, initiation of a new anticancer therapy, or the participant's or Investigator's decision to stop the treatment, whichever comes first. Each cycle of treatment will have a duration of 2 weeks. After discontinuing study intervention, participants will return to the study site approximately 30 days after the last IMP administration or before the participant receives another anticancer therapy, whichever is earlier, for end-of-treatment (EOT) assessments.

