9.2.1 General considerations

This study is not intended to explicitly test a hypothesis. For the primary and secondary efficacy endpoints, 95% CIs will be provided.

All efficacy endpoints based on radiological assessments of tumor burden (ie, ORR, DOR, PFS, and DCR) will be derived using the local radiologist's/Investigator's assessment.

In general, continuous data will be summarized using the number of observations available, mean, standard deviation, median, Q1, Q3, minimum, and maximum. Categorical and ordinal data will be summarized using the count and percentage of participants.

The baseline value is defined as the last available value before the first dose of IMP.

The study cut-off for analysis of the primary endpoint, ORR, corresponds to the date on which all evaluable treated participants have had at least 2 postbaseline tumor assessments, experienced confirmed objective response, or have discontinued the study treatment for any reason. For participants with 2 postbaseline tumor assessments and occurrence of response at the second postbaseline tumor assessment, it will also include the confirmatory assessment. This study cut-off can be up to approximately 20 weeks (16 weeks for 2 tumor assessments and 4 weeks for confirmation of response, if needed) after the last participant's first IMP administration. Of note, DCR will be also assessed at this cut-off.

The final study cut-off for analysis of the secondary efficacy endpoints, which include DOR and PFS, will be 4 months after the cut-off date for the primary analysis. At that time, the primary analysis of ORR and DCR will also be updated.

Observation period

The observation period will be divided into 4 segments:

- The **pre-treatment period** is defined as the period up to first IMP administration.
 - The **pre-screening period** is defined as the period from the pre-screening informed consent to the day before the screening informed consent.
 - The **screening period** is defined as the period from the screening informed consent up to the first IMP administration.

- The **on-treatment period** (ie, treatment-emergent period) is defined as the period from the first IMP administration to 30 days after the last IMP administration.
- The **post-treatment period** is defined as the period from the end of the on-treatment period.

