10.2 APPENDIX 2: CLINICAL LABORATORY TESTS

- The tests detailed in Table 9 will be performed by the local laboratory with the exception PK/Circulating CEACAM5, ATA, cfDNA/Germline DNA, and tumor DNA/RNA analysis and some additional circulating CEA, which will be performed in the central laboratory or another external laboratory.
- Protocol-specific requirements for inclusion or exclusion of participants are detailed in Section 5 of the protocol.

- Additional tests may be performed at any time during the study as determined necessary by the Investigator or required by local regulations.
- Pregnancy testing should be conducted in all WOCBP at Screening, then every 4 weeks from Cycle 2 before each IMP administration, and at the EOT, as detailed in the SoA (Section 1.3). Women of childbearing potential must have a negative serum pregnancy test result within 7 days prior to the initial intervention and at the EOT evaluation (30 ±5 days after the last IMP administration).

Laboratory tests	Parameters	
Hematology		
	Platelet count	
	Red blood cell (RBC) count	
	Hemoglobin	
	Hematocrit	
	White blood cell (WBC) count with differential:	
	Neutrophils ^a	
	Lymphocytes	
	Monocytes	
	Eosinophils	
	Basophils	
Coagulation	International normalized ration (INR)	
Clinical chemistry ^b		
	Urea or Blood urea nitrogen (BUN)	
	Creatinine-eGFR (estimated glomerular filtration rate)	
	Glucose	
	Potassium	
	Sodium	
	Phosphate	
	Chloride	
	Calcium	
	Aspartate aminotransferase (AST)/ Serum glutamic-oxaloacetic transaminase (SGOT)	
	Alanine aminotransferase (ALT)/ Serum glutamic-pyruvic transaminase (SGPT)	
	Lactate dehydrogenase (LDH)	
	Alkaline phosphatase (ALP)	
	Total and direct bilirubin	
	Total protein	
	Albumin	
	Circulating carcinoembryonic antigen (CEA) (local assessment)	
Pregnancy testing	Serum or highly sensitive urine human chorionic gonadotropin (hCG) pregnancy	
	test (as needed for women of childbearing potential) ^c	
Other screening tests	 Serology (Human immunodeficiency virus [HIV] antibody, hepatitis B surface antigen [HBsAg] or hepatitis B viral DNA, and hepatitis C virus antibody or Hepatitis C virus [HCV], RNA), and immunoglobulin G [IgG] if applicable as per local regulatory requirement 	

Table 9 - Protocol-required laboratory tests

27-Sep-2021	
Version number: 1	

Parameters
 Additional circulating carcinoembryonic antigen (CEA) and circulating CEACAM5 (central assessment)

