3.4.1.3 Time to deterioration

The time to deterioration (TTD), in disease related symptoms (cough, pain, dyspnea, fatigue, appetite) from NSCLC-SAQ, is defined as the time from baseline until the first \geq 2-point change from baseline (considered as clinically meaningful change) up to the end of treatment assessment before the analysis cutoff date (5). In case of missing score, no imputation will be done, and the assessment will be done according to the scales available.

Participants with a non-missing baseline assessment will be censored at the last on-treatment assessment before the start of further systemic anticancer therapy or before the analysis cutoff date (whichever is earlier), provided their symptoms scale had not deteriorated up to that point. Participant without baseline or post-baseline electronic patient-reported outcomes (ePROs) questionnaire or whose baseline scores do not allow further deterioration will be censored at the first IMP day.

TTD will only be analysed for the SAQ as there are no interpretation thresholds for the other measures.

TTD data will be summarized using the Kaplan-Meier method:

- Kaplan-Meier estimates of the 25th, 50th, and 75th percentiles and their associated 95% CIs will be provided. The 95% CIs will be constructed using a log-log transformation of the survival function and the method of Brookmeyer and Crowley.
- Number of participants at risks as well as the probabilities of being event-free at for example least 2, 4, 6, 8 ,10 months with 95% CIs will be estimated using the Kaplan-Meier method.
- The number of censored participants, the reasons and timing for their censoring (censored at first IMP administration, censored at last non-missing assessment before the initiation of a further systemic anti-cancer therapy, censored at last non-missing assessment before the cut-off date, censored at last non-missing on-treatment assessment). Kaplan-Meier curves will be plotted. These plots will include the number of participants at risk at key time points.

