3.6.3.2 Ocular examinations

Schirmer test

Participants reported Schirmer's test will be classified into three classes at baseline: normal ≥ 10 mm, moderate >5 and <10 mm, severe ≤ 5 mm (8). The worst classification between the laterality will be considered. A frequency table of the baseline status with and without anaesthetics will be provided by treatment group for the participants with corneal events (CMQ) during the treatment-emergent period and for the participants without event.

Visual acuity test

Analyses are done on the best corrected visual acuity assessed using Snellen Chart method.

Frequency tables on best corrected visual acuity (BCVA) measured during on-treatment period will be performed separately on all participants and on participants who experienced at least one treatment-emergent corneal event:

- on the worst change from baseline: No worsening versus baseline, Worsening versus baseline (1 to 3 lines decrease versus baseline, or >3 lines decrease versus baseline)
- on the worst absolute value: No change versus baseline, Worsening versus baseline: BCVA equals to 20/40 or better, BCVA worse than 20/40 up to 20/200, BCVA 20/200 or worse.

- on the CTCAE worst vision decrease: No worsening versus baseline, BCVA equals to 20/40 or better or 1 to 3 lines decrease versus baseline, BCVA worse than 20/40 up to 20/200 or >3 lines decrease versus baseline, BCVA 20/200 or worse.
- For participants who had worsening versus baseline on BCVA, the outcome on the last BCVA value will be displayed: Recovered to baseline, Not recovered to baseline, Lost to follow-up or dead with ongoing corneal events

A participant will be considered as lost to follow-up if the participant discontinued the study and did not perform any follow-up visit.

A shift table of the category of the last BCVA value (Normal (20/20 or better), worse than 20/20 up to 20/40, worse than 20/40 up to 20/200 or 20/200 or worse) versus the category of the worst BCVA value (20/40 or better, worse than 20/40 up to 20/200, 20/200 or worse) will be performed for participants who experienced at least one treatment-emergent corneal event.

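### The on-treatment period stops at day 30 after the last dose, but the EOT visit may fall as late as day 35, so on-treatment summaries, chiefly all-participants BCVA, exclude compliant EOT assessments made on days 31-35

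*SAP*

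**What the plan says.** **The period.** SAP 3.1 defines the on-treatment period in these words: "ie, treatment-emergent period) is defined as the period from the first IMP administration to 30 days after the last IMP administration". It thus treats it as the same thing as the treatment-emergent period. Protocol 9.2.1 has the same end point: "to 30 days after the last IMP administration".

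**The visit.** The protocol's flow chart (1.3.1) places EOT at "D30 after last infusion (±5 days". Protocol Appendix 2 (10.2) repeats the window for pregnancy testing: "at the EOT evaluation (30 ±5 days after the last IMP administration". Protocol 4.1 allows an earlier visit: "approximately 30 days after the last IMP administration or before the participant receives another anticancer therapy, whichever is earlier".

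**Where the period selects data.**
- SAP 3.6.3.2 covers "Frequency tables on best corrected visual acuity (BCVA) measured during on-treatment period", and adds that the all-participants table uses on-treatment values.
- SAP 3.6.3.1 takes worst laboratory, ECG and vital-sign values from the on-treatment or treatment-emergent period.
- SAP 3.4.1 limits post-baseline PRO assessments to the same 30 days, while also saying that visit statistics follow visits as recorded.
- SAP 3.6.3.3 refers to ECOG on treatment without naming the defined period.

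**A different end point for one PRO analysis.** SAP 3.4.1.3 runs time to deterioration "up to the end of treatment assessment before the analysis cutoff date", yet censors at the last on-treatment assessment.

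**The concern.** A site can keep to the schedule exactly and still have its EOT data classed as post-treatment. For assessments repeated every cycle this costs one late value. BCVA is different. Under protocol 8.2.2 the ophthalmologist examines participants at screening, at EOT and when indicated. For someone who never has a symptom-triggered exam, EOT is therefore the only post-baseline BCVA. If it falls on day 33, that person has no usable value in the all-participants table.

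SAP 3.6.3.2 gives no category for a missing post-baseline BCVA and does not say how such a participant is counted. The denominator shrinks or becomes ambiguous, and a late worsening could be missed. This matters because protocol 2.3.1 names corneal toxicity as the main anticipated risk.

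For PRO, two programmers could treat a deterioration first seen at a day-33 EOT visit differently, one as an event and the other as censored.

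**Working it through.** The plan gives no figure to reproduce here, so the check is a count of days and a comparison of sections.

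**Step 1: days outside the period.**
- Permitted EOT days (protocol 1.3.1 and 10.2): 30 − 5 = 25 to 30 + 5 = 35, which is 11 days.
- Last on-treatment day (SAP 3.1): day 30.
- Inside: days 25-30, 6 days. Outside: days 31-35, 5 days. 5/11 = 45.5%.

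**Step 2: is there a rule that brings days 31-35 back?** SAP 3.1 has no visit-assignment clause. SAP 5.4 (data handling) deals only with unscheduled visits. SAP 3.9 lists no change. The cut-off rules in SAP 3.8 extend the period only for participants with no EOT visit yet. None was found.

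**Step 3: how many visits?** The documents do not give the spread of EOT dates, so each line is an assumption applied to the 38 planned participants.

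| Assumed spread | Share on days 31-35 | Of 38 |
|---|---|---|
| Low share | 10% | 3.8 (about 4) |
| Moderate share | 25% | 9.5 |
| Triangular, peak at day 30 | 15/36 = 41.7% | 15.8 (about 16) |
| Uniform | 5/11 = 45.5% | 17.3 (about 17) |
| High share | 60% | 22.8 (about 23) |

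The triangular weights are 1, 2, 3, 4, 5, 6, 5, 4, 3, 2, 1 (sum 36); days 31-35 carry 5 + 4 + 3 + 2 + 1 = 15. At the interim analysis the uniform case gives 20 × 5/11 = 9.1 of 20.

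**Step 4: how many would have no post-baseline BCVA?** Only those without an on-treatment symptom-triggered exam. As an illustration, suppose the 30.1% corneal TEAE rate in protocol Table 1 (56/186) marks the participants who had such an exam. The uniform case then leaves 17.3 × (1 − 0.301) = 12.1, about 12.

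**Step 5: which analyses are cut at day 30?**

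| Analysis | Position |
|---|---|
| BCVA, all participants (3.6.3.2) | Cut; EOT may be the only value |
| Worst laboratory, ECG, vital signs (3.6.3.1) | Cut; one late value among many |
| PRO (3.4.1) | Cut by the 30-day rule; in conflict with 3.4.1.3 |
| ECOG (3.6.3.3) | Cut only if on treatment means the defined period |
| ECG and vital signs by planned visit (3.6.3.1) | Unclear |
| BCVA in participants with corneal events (3.6.3.2) | Event start and end dates used; lead-in says on-treatment |
| Slit lamp (3.6.3.2) | Tied to the corneal event |
| Schirmer (3.6.3.2) | Baseline only |
| Liver-test recovery (3.6.3.1) | Includes values after the last dose |
| ATA (3.7.1.2) | Any time after IMP |

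**Step 6: coverage after the change.** Counting EOT to day 35 covers 11 of 11 permitted days, against 6 of 11 now.

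**The case against.** The strongest reply is about scope and harm. A reader might infer that late EOT data vanish from the ocular, laboratory, ECG, ECOG and PRO analyses altogether. The last table above shows otherwise. Nor is a late finding lost to the report: if it is recorded as an AE, SAP 3.6.2 has separate post-treatment AE and SAE tables. Laboratory tests, ECG, ECOG and PROs are repeated every cycle, so one missing value will seldom change a worst-value table. Symptoms are checked before each infusion, and any ocular symptom triggers complete ocular tests, so symptomatic participants will usually have other BCVA values.

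A reader might also infer that asymptomatic vision loss is being undercounted. The documents do not show this. In protocol Table 10, Grade 1 keratopathy is asymptomatic with lesions only, and reduced acuity begins at Grade 2, which is symptomatic. The lost records may be mostly normal or near-normal, which is a denominator problem first.

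All of this stands and narrows the point. It does not remove it. The summaries tied to corneal events require a treatment-emergent event, and a lesion first found and dated at a day-33 visit is a post-treatment AE. Those summaries therefore do not recover a participant whose only finding came at a late EOT exam.

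**Conclusion.** The mismatch is real and follows from the text: 5 of 11 permitted EOT days lie outside the on-treatment period, with no rule to assign them. The material consequence is in the all-participants BCVA tables. There, a participant without a symptom-triggered exam and with EOT on days 31-35 has no post-baseline value, so the denominator falls and a late worsening may be missed. The effect on worst laboratory, ECG and vital-sign values is small. The effect on ECOG depends on what on treatment means. For PRO the added problem is the conflict between SAP 3.4.1 and 3.4.1.3.

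The count of affected visits is an assumption. About 17 of 38 is the result of an even spread and should not be read as a maximum; shares of 10% to 60% give about 4 to 23. All these figures suppose that every participant attends EOT within the window. They fall when EOT is brought forward for new therapy, or when a participant dies or withdraws first.

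The study is single-arm and descriptive, and ORR, PFS, DOR and DCR are not touched. The correction is worth making before the analyses are programmed, but it does not put the main result at risk.

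**What to change.** - In SAP 3.1, 3.4.1 and 3.6.3, state that for visit-based assessments the scheduled EOT visit counts as on-treatment if it takes place by day 35 and before new anticancer therapy. At minimum, apply this to BCVA and PRO.
- Keep 30 days for TEAE onset.
- Reconcile SAP 3.4.1 with 3.4.1.3, so that time to deterioration has one end point and one censoring rule.
- Within SAP 3.6.3.2, reconcile the on-treatment lead-in with the event-date window used for participants with corneal events.
- Record the change in SAP 3.9, now marked not applicable. Protocol 9.2.1 has the same 30-day definition, and protocol 9.2.5.2 ties worst laboratory, ECG and vital-sign values to the treatment-emergent period.

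The cost is a few sentences and one entry in SAP 3.9, with no new data or visits. The downside is that visit-based data and TEAEs would use slightly different windows: a value on days 31-35 could count as on-treatment while a matching AE counts as post-treatment. A footnote on the affected tables would make that plain.
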